7.2.1. Outcomes Research Endpoints

For the outcome research endpoints, rules for scoring and handling of missing data suggested by the developers will be followed.

7.3. Missing Data due to COVID-19 Pandemic

Because of the COVID-19 pandemic, some scheduled on-site visits may be substituted by remote visits such as telephone contacts. The data collected via the remote visits will be treated the same as the data collected by the on-site visits.

Missing data due to COVID-19 pandemic will be handled the same as that for other missing data.

In addition, the following summaries will be provided.

- Discontinuation due to COVID-19 impact will be reported in the disposition table.
- Missed visits due to COVID-19 impact are recorded as PD and will be in the specific PD tables in the Clinical Study Report (CSR).
- A set of summary/listing tables based on a subset of protocol deviations associated with COVID-19 will be provided. Study drug discontinuation, subject discontinuation due to COVID-19 and adverse events related to COVID-19 will be summarized as well. The source information will be captured in the protocol deviation.

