6.2.1. Visit Windows

The screening period is expected to be no longer than 4 weeks in duration, unless exceptions noted in [Section 6.1](#) are documented, with the Baseline visit (Day 1) occurring within the 28 days following the day that the subject signs the informed consent.

All other visits (Visits 2-22) should be conducted as close to the scheduled visit day as possible. Exceptions may be made to accommodate holidays and unexpected events, such as weather-related site closures or illnesses requiring hospitalization. In these cases, the visit should be scheduled or re-scheduled as close to the original visit schedule as possible.

All visits will contribute to the dataset. The visit window for Visit 2 (Month 2) is ± 2 weeks; all other visit windows are ± 1.5 months to ensure capture of all data.

Partial visits (ie, those that do not include all required procedures) must be noted clearly and the reason documented in the subject's case report form.

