8.2.2. Analyses of Other Safety Endpoints

The analyses will be based on the Safety Analysis Set. The 28-Day On-Treatment Time will be applied to all the events of interest, see [Section 7.1.1](#).

The times to the secondary endpoints of opportunistic infection events excluding tuberculosis, tuberculosis, hepatic events, cardiovascular events (MACE and others), serious infections, GI perforations, non-melanoma skin cancers, interstitial lung disease, DVT, PE, ATE, DVT or PE, thromboembolic events (TE) and all-cause mortality will be analyzed by Cox models via univariate model analysis. See [Section 8.1.1](#). The 28-Day On-Treatment Time analysis will be conducted.

The times to herpes zoster events will be analyzed by a multivariate Cox model with region, baseline corticosteroid use, age group, smoking status, treatment as predictors. The 28-Day On-Treatment Time analysis will be conducted.

Unadjusted, or “crude” incidence rates will be calculated as well. Note that the ratios of these rates approximate, but are not exactly equal to, the hazard ratios.

A Surveillance, Epidemiology, and End Results (SEER) analysis of the malignancy endpoint will be conducted. In this analysis, standardized incidence ratio (SIR) for malignancies represents the ratio of the incident number of cases of cancer in the tofacitinib population to the incident number that would be expected if the study population had the same incidence rate as the US population. By way of interpretation, a SIR of more than 1.0 indicates that proportionally more cases of cancer have occurred in the tofacitinib population than the comparator, whereas a SIR of less than 1.0 indicates that proportionally fewer cancer cases have occurred.

The Sponsor has standard (ie, used for all its clinical trials) summary displays and listings for MedDRA-coded adverse events, demography, medical history, length of time in study and discontinuation, concomitant and concurrent medications, physical examination, ECG, laboratory tests, weight, pulse rate, and blood pressure. These standards, called *CaPS (CDISC and Pfizer Standards)*, will be utilized in the reporting of these routine safety variables. For laboratory tests total cholesterol, LDL-c, HDL-c, total cholesterol/HDL-c ratio, LDL-c/HDL-c ratio, Triglyceride, the summary will be produced by subjects on statins, subjects not on statins and subjects on any lower lipid agents including statins.

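### SAP 7.3 names only the protocol-deviation record as the source for its COVID-19 adverse-event summary, so COVID-19 events without a linked deviation could be missing from that table

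*SAP*

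**What the plan says.** SAP 7.3 lists the extra pandemic summaries in three bullets.

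- The first deals with discontinuation: "Discontinuation due to COVID-19 impact will be reported in the disposition table".
- The second deals with visits: "Missed visits due to COVID-19 impact are recorded as PD", with tables of these in the study report.
- The third opens with "A set of summary/listing tables based on a subset of protocol deviations associated with COVID-19 will be provided". It then adds that study drug discontinuation, subject discontinuation and "adverse events related to COVID-19 will be summarized as well. The source information will be captured in the protocol deviation".

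Section 7.3 mentions no adverse-event dataset, coded-term search or CRF flag for COVID-19 events. No other SAP section defines a COVID-19 adverse-event analysis.

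Routine adverse-event reporting follows a different path. Protocol 8.13.2 puts every adverse event on the AE page of the CRF, and Protocol 8.2 sets the recording period from first dose to the last subject visit. SAP 8.2.2 then reports them through the sponsor's "standard (ie, used for all its clinical trials) summary displays and listings for MedDRA-coded adverse events". Protocol 13.4 describes deviations as a separate log kept by the monitors.

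**The concern.** A deviation log records departures from the protocol; an adverse-event record shows what happened to the subject's health. A table of COVID-19 illness drawn from the first would hold only those cases that also disturbed trial conduct. Cases would enter according to whether a visit or procedure went wrong, not according to the illness.

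Protocol 1.2 lists infection among the identified risks of tofacitinib, so readers will look at a COVID-19 table by arm. If it is incomplete by construction, its counts may not match the COVID-19 terms in the main adverse-event tables of the same report, and a reader could not tell which to use.

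**Working it through.** The documents give no figure on this point, so the check sets the text side by side. The question is whether a COVID-19 illness must leave a deviation record under the documents as written.

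1. **Missed visits.** This is the only COVID-19 occurrence that SAP 7.3 says is recorded as a deviation. An illness that causes no missed visit is not covered by that statement.

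2. **Visit timing.** Protocol 6.2.1 says of visits after Month 2 that "all other visit windows are ± 1.5 months to ensure capture of all data". From Month 3 visits are 3 months apart, and a window of ±1.5 months is 2 × 1.5 = 3 months wide, so successive windows meet. The same section accepts rescheduling for illness that needs hospitalization. An ill subject can therefore be seen late and still within the plan.

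3. **Remote contact.** SAP 7.3 treats data from telephone or other remote visits like data from on-site visits, and does not say that a remote visit is a deviation.

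4. **Withheld doses.** Protocol 5.3.5 states that doses not taken while drug is withheld for an adverse event are not deviations.

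5. **Serious infection.** Protocol 7.15 and 8.4.2 call for study drug to be interrupted during a serious infection. A subject whose drug is interrupted for serious COVID-19 is being managed as the protocol requires.

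6. **Permanent withdrawal of drug.** Protocol 8.11 provides for withdrawal of assigned drug because of an adverse event, with the subject staying in the study. That, too, follows the protocol.

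From 1 to 6, a COVID-19 illness can be mild or serious, with or without interruption or withdrawal of drug, and leave no deviation that these documents define.

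**Consequence for the summary.** If the deviation record is the source of cases, an event without a deviation never enters. If the deviation record supplies only the note linking an event to COVID-19, the outcome is the same, because without a deviation there is no note.

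**What is not lost.** The same event is still on the AE page of the CRF. It appears in the routine tables if it is treatment-emergent (SAP 8.2.2). If it is a serious infection within the 28-day on-treatment window, it enters the Cox analysis of serious infections (SAP 7.1.1 and 8.2.2). Infections, serious infections, serious adverse events and deaths are also analysed by age (SAP 8.2.5).

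**Size.** The share omitted is 1 − P(a deviation is logged, given a COVID-19 adverse event). The documents give neither that probability nor the number of COVID-19 events, so no estimate follows.

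**The case against.** The strongest reply is that SAP 7.3 never says adverse-event data will not be used. Its source sentence follows a sentence covering three items, two of them discontinuations, and the first bullet already reports COVID-19 discontinuation in the disposition table. For that item the deviation record is evidently not the only route, so the source sentence may be loose wording about where the link to COVID-19 is documented. This stands in part: a reader might infer that the SAP replaces the adverse-event data with deviation records, and the text does not go that far. What remains is that the deviation record is the only source stated for the adverse-event item, and no other bullet or section supplies a second route for it.

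A second reply is that deviations are defined by sponsor procedures and by a list of potentially important deviations that is updated during the study (Protocol 13.4, SAP 5.5), neither of which is in the documents. Sites may have logged COVID-19 events as deviations. That is possible and cannot be checked, so disagreement with the main tables is a risk and not a certainty.

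A third reply is that the safety information is reported elsewhere. That is correct, within the treatment-emergence and 28-day rules that apply to other events, and it is the main reason to rate the point low.

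**Conclusion.** The point holds as a reporting defect in one descriptive summary. Read literally, SAP 7.3 would leave out COVID-19 adverse events that have no linked deviation, including serious ones. This rests on two assumptions: that the source sentence applies to the adverse-event item as written, and that no unseen sponsor rule makes every COVID-19 illness a deviation.

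Two stronger readings are not supported. A reader might infer that COVID-19 cases are lost to the trial's safety evaluation; they are not, because adverse-event recording does not depend on deviations. A reader might also try to size the omission by dividing an assumed illness length by the spacing of visits. The documents give no illness length, rescheduling breaks the link between illness and a missed visit, and other COVID-19 deviations, such as procedures not done, would be ignored.

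The MACE and malignancy analyses are unaffected. SAP 8.2.2 plans no inferential analysis for the routine safety displays. Severity is low.

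**What to change.** Amend the third bullet of SAP 7.3 along these lines:

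*COVID-19 adverse events are identified from the AE/SAE database with a pre-specified list of MedDRA terms, together with any event linked to COVID-19 in the deviation record. They are summarized by randomized group, whether or not a deviation was logged.*

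Keep deviations as the source for missed or remote visits and for procedures not done. Take discontinuations from the disposition data, as the first bullet of 7.3 already states, so that the bullets agree.

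Keeping events linked through the deviation record matters because events related to COVID-19 may be broader than coded infection, and a term list alone could miss some of them.

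The cost is small: one edit to the SAP, a term list to maintain, and reconciliation of that list with the deviation log. No new data collection is needed, since adverse events are already recorded on the CRF and MedDRA-coded.

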8. STATISTICAL METHODOLOGY AND STATISTICAL ANALYSES

In general, number and percent will be presented for binary variables, number, mean, standard deviation (standard error of the mean), minimum, 1st, 2nd and 3rd quartiles and maximum will be presented for continuous variables. In addition, graphics may be used to present the data.

8.1. Statistical Methods

8.1.1. Analyses of Time-to-Event Data

Comparisons of hazard functions in time-to-event analyses will be carried out via (linear) Cox proportional hazard models. Censoring conventions are given in [Section 7](#). A univariate analysis model containing only the single independent variable for treatment group will be calculated and reported.

In addition, the effects of adding other predictors to the Cox model, such as geographic region, age group, gender, and smoking status will be fully explored and reported.

8.1.2. Analyses of Incidence Rates

Crude incidence rates will be reported as the total number of subjects with admissible events divided by the total (for all qualifying subjects) time at risk for the cohort/treatment group of interest. For subjects with events, the time at risk will be the time to the first event, for subjects without events, it will be the censoring time defined in [Section 7.1.1](#).

When subjects change regimens from study medication to standard of care then the following counting rules will be used to account for group changes in the estimation of crude incidence rates (where applicable):

- For MACE: there will be a 60-day risk window during which events will be attributed to both treatment groups, after which they will be assigned to the current treatment group.
- Malignancies (excluding NMSC): there will be a 60-day risk window during which events will only be attributed to the prior treatment group, after which they will be assigned to both treatment groups.

The 95% CIs for the crude incidence rate will be calculated for incidence rates based on the assumption that the actual count of cases arises from a Poisson distribution. The approach used in Daly et al.^{2,3} describing the calculation of exact confidence limits will be used. If x denotes the actual number of subjects with events, $(1 - \alpha)$ denotes the confidence level, x_L denotes the lower confidence limit and x_U denotes the upper confidence limit, then the following formula yields values for x_L and x_U ,

When $x > 0$,

$$x_L = 0.5 * \chi^2(2x; \alpha/2) \text{ and } x_U = 0.5 * \chi^2(2x+2; 1-\alpha/2),$$

When $x = 0$,

$$x_L = 0 \text{ and } x_U = 0.5 * \chi^2(2x+2; 1-\alpha/2).$$

In the above notation, $\chi^2(n; p)$ represents the p^{th} quantile of the chi-square distribution with n degrees of freedom.

Once x_L and x_U are obtained, they are to be adjusted for the at-risk population per 100 subject-years by multiplying by (100/total subject-years of event exposure).

Indirect standardization will also be used in a second analysis of malignancy data. With indirect standardization, age and sex-specific cancer rates in a standard population (ie, general US population via the Surveillance Epidemiology and End Results [SEER] registry) are used as weights for person-time of the age and sex-specific subgroups in the tofacitinib trial population. The resulting standardized incidence ratio (SIR) represents the ratio of the incident number of cases of cancer in the tofacitinib population to the incident number that would be expected if the study population had the same incidence rate as the US population. The SIR along with the 95% CI will be calculated for the adjudicated malignancies excluding NMSC and each cancer type (corresponding to the ones where the SEER incidence rates are available) for each randomized tofacitinib group (not for the TNFi group). For each cancer type and each treatment group, the expected number of cancer cases will be calculated as the SEER incidence rate (cancer type specific incidence rates) multiplied by the person-time (cancer type specific person-time) of each age (age categories according to SEER) and sex combination summed over all the age and sex combinations. The detailed calculation is provided in [Appendix 2.2](#).

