The DSMB stated they also believe that the risk-benefit profile of tofacitinib 5 mg BID in comparison to TNFi control remains appropriately balanced, and that the scientific question of evaluating the safety of tofacitinib 5 mg BID versus TNFi with respect to the co-primary and secondary safety endpoints in Study A3921133 is worthwhile and important.

For this reason, the DSMB has recommended modifying Study A3921133 to discontinue treatment with tofacitinib 10 mg BID. They further recommended that patients in the tofacitinib 5 mg BID and TNFi control treatment arms should continue to receive their assigned treatments.

Pfizer has accepted this recommendation and with Amendment 8 is modifying the tofacitinib 10 mg BID treatment arm accordingly. Investigators were instructed to contact all subjects taking tofacitinib 10 mg BID within 7 calendar days and verbally inform them of this information, secure their verbal agreement to continue in the study and if they agreed, reduce their dose of tofacitinib to 5 mg BID. This amendment documents these changes and requires all subjects to sign the Addendum to the Informed Consent Document at their next study visit, explaining the safety information and secure their agreement to continue in the study.

The comparator TNFi, adalimumab, is reported to be associated with risks of infection, malignancy, anaphylaxis or serious allergic reactions, demyelinating disease, cytopenias, pancytopenia, heart failure, and Lupus-like syndrome. The identified risks for adalimumab in RA are presented in the Humira® (adalimumab) United States Package Insert (USPI), content revised January 2019.

The comparator TNFi, etanercept, is reported to be associated with risks of infection, malignancy, demyelinating disease, lymphoma, congestive heart failure, pancytopenia or aplastic anemia, anaphylaxis or serious allergic reactions, Lupus-like syndrome or autoimmune hepatitis. The identified risks for etanercept in RA are presented in the Enbrel® (etanercept) EU SmPC, revised October 2017.

Complete information for tofacitinib may be found in the Single Reference Safety Document (SRSD), which for this study is the XELJANZ™ (tofacitinib citrate) Investigator Brochure, Section 7.8 Undesirable Effects (All indications); the Single Reference Safety Document for the comparator agent, adalimumab, is the USPI, revised January 2019; the Single Reference Safety Document for etanercept is the EU SmPC, revised October 2017.

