 - h. Subjects are excluded for current active tuberculosis infection or prior active or latent tuberculosis that was inadequately treated or cannot be documented (See [Section 4.1 Inclusion Criteria #13](#)).
5. Subjects with any current malignancy or a history of malignancy, with the exception of adequately treated or excised non-metastatic basal cell or squamous cell cancer of the skin or cervical carcinoma in situ.
 6. Subjects with any uncontrolled clinically significant laboratory abnormality or any of the following laboratory abnormalities (For additional Sweden-specific laboratory criteria, see [Appendix 4](#) and Czech Republic, Spain and United Kingdom-specific laboratory criteria, see [Appendix 5](#)):
 - a. Evidence of hematopoietic disorder or hemoglobin <9 g/dL.
 - b. White blood cell count <3.0 x 10⁹/L (<3000/mm³).
 - c. Absolute lymphocyte count <0.5 x 10⁹/L (<500/mm³).
 - d. Absolute neutrophil count <1.0 x 10⁹/L (<1000/mm³).
 - e. Platelet count <100 x 10⁹/L (<100,000/mm³).
 - f. Alanine aminotransferase (ALT), or aspartate aminotransferase (AST) >1.5 times the upper limit of normal (x ULN).
 - g. Estimated glomerular filtration rate (GFR) <60 mL/min using the Cockcroft-Gault formula ([Appendix 3](#)).
 7. Participation in other studies involving investigational drug(s) (Phases 1-4) within 4 weeks or 5 half-lives (whichever is longer) after discontinuation of the investigational compound before the current study begins and/or during study participation, unless further restrictions to class of compound are specified in [Section 4.2 Exclusion Criteria](#) and [Section 5.5 Concomitant Medication\(s\)](#).

8. Subjects requiring or have received any prohibited concomitant medication as outlined in [Appendix 2](#), including:
 - a. Subjects who have received live or live attenuated vaccines within 6 weeks prior to the first dose of study drug or at any time during treatment or within 6 weeks following discontinuation of study drug (See [Section 4.4.2](#)).
 - b. Subjects who have been previously treated with tofacitinib.
 - c. Subjects who are being treated with biologic or non-biologic DMARDs other than MTX or antimalarials within their specified washout window at study entry (see [Table 1](#)).

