9.2. Safety Analysis

9.2.1. Analysis of Primary Safety Endpoint

The co-primary safety endpoints of malignancies and MACE will be analyzed to provide comparative rates for tofacitinib vs. the combined TNFi.

The primary statistical safety objective is the estimation of the hazard ratios relative to the TNFi control for the two tofacitinib doses combined and for each dose of tofacitinib separately for the adjudicated events of MACE and malignancy excluding non-melanoma skin cancer. Analysis of the primary safety endpoints will be based upon adjudicated events.

Hazard ratios for the safety events of main interest will be calculated separately for each primary endpoint. The ratios for both tofacitinib doses combined versus the control, for each tofacitinib dose versus the control, and for the two tofacitinib doses versus each other will be reported along with their 95% confidence intervals. Adjustments for multiplicity will not be applied.

The primary statistical method for deriving estimators for hazard ratios will be the fitting of proportional hazards (Cox) regression models. A model containing only the single independent variable for treatment group will be calculated and reported. The effects of adding other predictors to the model, such as geographic region, age, gender, and so forth will be fully explored and reported. An analysis by TNFi subset strata (ie, the sites/regions where either adalimumab or etanercept was used) will be conducted to assure consistency of results.

A Surveillance, Epidemiology, and End Results (SEER) analysis of the malignancy endpoint will be conducted.

Both total time (or ITT) and on treatment analyses of the main safety endpoints will be conducted. The total time analysis will not censor times to event and will ascribe events to randomized treatment.

The on-treatment analysis for MACE will censor subjects who crossover from tofacitinib, adalimumab or etanercept to standard of care at 60 days after standard of care is initiated. The principal analysis for malignancies will not censor for subjects crossing to standard of care (ie, will be the total time analysis).

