Appendix 2.2. Further Details of the Statistical Methods

Definition of the SIR

Suppose the person-time from a treatment group is allocated among M subgroups defined by the cross-classification of sex and age group. Let t_k represent the person-time for that subgroup and D_k represent the observed number of subjects with events in the k th subgroup, and let λ_k^* represent the SEER incidence rate for the k th subgroup, where $k = 1, 2, \dots, M$. Given this notation, the SIR is defined as:

$$\text{SIR} = \frac{\sum_{k=1}^M D_k}{\sum_{k=1}^M t_k \lambda_k^*} = \frac{D}{E^*}$$

where the total number of subjects with events observed in the treatment group is

$D = \sum_{k=1}^M D_k$, and the expected total number of subjects with events is

$E^* = \sum_{k=1}^M E_k^* = \sum_{k=1}^M t_k \lambda_k^*$ (Breslow and Day, 1987;⁴ Sahai and Khurshid, 1996).⁵

Exact Confidence Limits for the True SIR

Sahai and Khurshid (1993,⁶ 1996)⁵ discuss the following method for obtaining the exact confidence limits, SIR_L and SIR_U , for the true SIR, ϕ . Assuming D is Poisson distributed with mean $\mu = E(D)$, confidence limits for μ are obtained using the relationship between the Poisson distribution and the chi-square distribution. Then these limits are divided by the expected total number of subjects with events, E^* , to obtain the limits.

$$\text{SIR}_L = \frac{\chi_{2D, \alpha/2}^2}{2E^*} \quad \text{and} \quad \text{SIR}_U = \frac{\chi_{2(D+1), 1-\alpha/2}^2}{2E^*}$$

where $\chi_{v, \alpha}^2$ is the $100 * \alpha$ percentile of the chi-square distribution with v degrees of freedom.

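### The SEER standardized incidence ratio is planned for tofacitinib only, leaving the type-specific cancer results without a randomized control, and the sentence interpreting 1.0 is ambiguous

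*SAP*

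**What the plan says.** SAP 8.1.2 introduces the method with "Indirect standardization will also be used in a second analysis of malignancy data". The expected count is the number of cancers that would occur "if the study population had the same incidence rate as the US population", built from age- and sex-specific SEER rates. The SIR and its 95% CI are to be produced for adjudicated malignancies excluding non-melanoma skin cancer (NMSC), and for each cancer type with a SEER rate, "for each randomized tofacitinib group (not for the TNFi group". No reason is given for leaving TNFi out.

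Two other places are broader. Protocol 9.2.1 says "A Surveillance, Epidemiology, and End Results (SEER) analysis of the malignancy endpoint will be conducted", with no restriction by arm. SAP Appendix 2.2 opens its formula with "Suppose the person-time from a treatment group is allocated among M subgroups defined by the cross-classification of sex and age group", which applies to any arm.

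On interpretation, SAP 8.2.2 again defines the SIR against the US population and then says that "a SIR of more than 1.0 indicates that proportionally more cases of cancer have occurred in the tofacitinib population than the comparator".

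**The concern.** An SIR compares trial subjects with an external population, so 1.0 marks the absence of a drug effect only if trial subjects would otherwise have US cancer rates for their age and sex. Several design features argue against that. Protocol 4.2 excludes "Subjects with any current malignancy or a history of malignancy", with limited exceptions. All subjects have RA, SAP 6.4 lists four geographic regions, and Protocol 4.1 accepts current smoking as a qualifying cardiovascular risk factor. Age-sex standardization removes none of these.

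The TNFi arm passed through the same selection and would show where the baseline lies. Without it, a tofacitinib SIR near 1.0 can be neither reassuring nor alarming about the comparison with TNFi.

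The exposure is greatest for individual cancers. SAP 8.2.1 analyses malignancy as one composite, and the Cox endpoints in 8.2.2 include NMSC but no other single cancer type. The standard adverse event tables are by randomized group, but the SAP plans no inference from them.

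The wording adds a second risk. The protocol uses *comparator* for the control drugs ("The comparator TNFi, adalimumab, is reported to be associated with risks of infection"), so a reader could take an SIR below 1.0 to mean fewer cancers than on TNFi.

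**Working it through.** **1. The plan's own figure.** The documents state no SIR, SEER rate or expected count. The relevant design figure is 138 malignancies (Protocol 9.1: margin 1.8, two-sided 95%, 90% power, true hazard ratio 1.0), with 1:1:1 allocation, so one third of subjects are on TNFi. Schoenfeld's formula gives (1.960 + 1.282)² / [(1/3)(2/3)(ln 1.8)²] = 10.51 / 0.0768 = 137. The stated 138 is reproduced to within one event and gives power 0.902. With equal rates, each arm contributes 138/3 = 46 malignancies.

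**2. What a tofacitinib SIR of 1.0 implies.** By Appendix 2.2, SIR = D/E*. Randomization should give the arms a similar age-sex mix, so the expected count per person-year is about equal in each. Then SIR(tofacitinib) / SIR(TNFi) approximates the ratio of cancer rates. Write b for the TNFi SIR:

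SIR(tofacitinib) ≈ b × HR, so SIR(tofacitinib) = 1.0 implies HR ≈ 1/b.

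The documents do not give b. Over an assumed range of 0.5 to 1.2:

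| b (assumed) | Tofacitinib/TNFi ratio when the tofacitinib SIR is 1.0 |
|---|---|
| 0.5 | 2.00 |
| 0.6 | 1.67 |
| 0.7 | 1.43 |
| 0.8 | 1.25 |
| 0.9 | 1.11 |
| 1.0 | 1.00 |
| 1.1 | 0.91 |
| 1.2 | 0.83 |

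At b = 1/1.8 = 0.56, a tofacitinib SIR of 1.0 would coincide with the 1.8 non-inferiority margin.

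**3. How well the TNFi arm could measure b.** Exact Poisson limits, as multiples of the estimate:

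- 46 events (overall): 0.5 × χ²(0.025; 92)/46 = 0.73 and 0.5 × χ²(0.975; 94)/46 = 1.33.
- 5 events (an assumed count for one cancer type): 0.5 × χ²(0.025; 10)/5 = 0.32 and 0.5 × χ²(0.975; 12)/5 = 2.33.

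Two worked cases with 46 TNFi events:

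- b = 0.8: E* = 46/0.8 = 57.5, and the TNFi SIR is 0.80 (0.59 to 1.07). The interval includes 1.0.
- b = 0.7: E* = 46/0.7 = 65.7, and the TNFi SIR is 0.70 (0.51 to 0.93). A tofacitinib arm with the same E* and HR 1.43 has 66 events and an SIR of 1.00 (0.78 to 1.28).

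In the second case the planned output would show only the 1.00. With the TNFi column beside it, the reader would also see the 0.70.

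**The case against.** The strongest reply is that the question of excess malignancy is already answered by randomization. SAP 4.2 and 8.2.1 rest it on the Total Time Cox hazard ratio against TNFi. Covariate-adjusted models, an analysis by TNFi stratum and crude incidence rates support it. The SIR is a second analysis and enters no decision rule. For the overall endpoint, the ratio of the two SIRs would largely repeat the primary comparison in a less direct form. This stands, and it is why the point is minor.

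It also stands that type-specific TNFi SIRs would be imprecise, and that even 46 events calibrate only modestly. This limits the gain but does not remove it: an imprecise randomized control shown with its interval is more informative than none.

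Three stronger readings are tempting, and the documents do not support them.

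- *That the SAP misreads 1.0.* A reader might infer this from the sentence in 8.2.2. The sentence before it sets the US population as the reference, and against that reference the statement is arithmetically right. The SAP nowhere says that an SIR of 1.0 means no drug effect or parity with TNFi. The fault is ambiguity.
- *That the tofacitinib-only SIR hides an excess.* The direction is unknown. Excluding cancer history may lower the baseline, recruiting smokers may raise it, and region may act either way. An overall excess over TNFi would in any case be estimated by the hazard ratio.
- *That the malignancy endpoint has no internal reference.* This is true of the SIR alone.

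**Conclusion.** The point holds as a minor gap in a supportive analysis. As planned, the SIR cannot say how tofacitinib compares with TNFi: a value of 1.0 is compatible with ratios from 0.83 to 2.00 over the assumed baseline range of 0.5 to 1.2. That range is an assumption and not a finding, and the calculation also assumes a similar age-sex mix across arms.

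No primary conclusion, event target or power changes. The practical consequence falls on individual cancer types other than NMSC, where the tofacitinib-only SIR is the only type-level analysis with intervals that the SAP names. The TNFi SIR would also not be a drug-free baseline, because Protocol 1.2 lists malignancy among the reported risks of both control drugs. It calibrates against TNFi, which is the comparison the trial was designed to make.

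**What to change.** 1. In SAP 8.1.2, delete the parenthesis that leaves out the TNFi group. Compute overall and type-specific SIRs with exact 95% CIs for TNFi by the Appendix 2.2 method.
2. In SAP 8.2.2, replace *the comparator* with *the general US population*.
3. Add a statement that the SIR is descriptive and does not compare treatments, and that each tofacitinib SIR is read alongside the TNFi SIR and not against 1.0 alone. Note the limited precision: about 0.73 to 1.33 times the estimate at 46 TNFi events, and much wider by type.

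The cost is one more column from a program already specified and a few changed sentences. No new trial data are needed, and no decision rule changes.
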